## 7. PLANNED ANALYSIS

For End-Of-Text (EoT) tables, the set of summary statistics is: N / Mean / SD / SE / Min / Q1 (lower quartile)/ Median / Q3 (upper quartile)/ Max. The 1st and 99th percentiles might be substituting minimum and maximum in tables with open-ended values to safeguard against implausible extremes.

Geometric means and ranges will be added to the presentation or replace the presentation of mean and standard deviation for parameters which rather follow a log-normal distribution than a normal distribution.

Statistical parameters will be displayed to a defined number of decimal places as specified in the BI guideline “Reporting of Clinical Trials and Project Summaries” (4)

Tabulations of frequencies for categorical data will include all possible categories and will display the number of observations in a category as well as the percentage (%) relative to the respective treatment group (unless otherwise specified, all patients in the respective patient set whether they have non-missing values or not). Percentages will be rounded to one decimal place. The category missing will be displayed only if there are actually missing values.

Disposition of the patient population participating in the trial will be analysed by treatment groups and presented in the clinical trial report as a frequency-distribution.

Disposition as required for reporting for the trial in EudraCT will be provided. Enrolment will be summarised by country and by age group for reporting in EudraCT. (see (13)).

Number of patients lost to follow up (no information on vital status after start of study closure) and number of patients lost to follow up for the primary endpoint (no information on primary endpoint after start of study closure) will be summarised.

The reason for not randomising screened patients will be summarized descriptively.

The frequency of patients with IPDs will be presented by treatment group for the randomised set. The frequency of patients in different analysis sets will also be analyzed for each treatment group.

### 7.1 DEMOGRAPHIC AND OTHER BASELINE CHARACTERISTICS

Demographics and baseline characteristics will be analyzed based on RS. Demographics will be repeated on the TS if the analysis sets differ by more than 1%. Standard descriptive analysis and summary tables will be presented. These summary tables will include description of subgroup variables detailed in Section 6.4. Descriptive analysis of the following variables measured at baseline will be presented: Age, body mass index (BMI), time since diagnosis, systolic blood pressure (SBP), diastolic blood pressure (DBP), heart rate, weight, eGFR, UACR, NT-pro BNP, LVEF, hemoglobin and troponin T. HbA1c will be presented for patients with diabetes at baseline. NTproBNP will be shown for patients with or without atrial fibrillation/ atrial flutter at baseline.

A summary of the number of patients in each randomisation stratum per treatment will also be shown. The information will be based upon the data received from the interactive voice

response system (IVRS) provider. Analyses will be based on actual information collected via the CRF / central laboratory, not via IVRS.

## **7.2 CONCOMITANT DISEASES AND MEDICATION**

Only descriptive statistics are planned for this section of the report using the randomised set. Concomitant medication use will be summarised by Anatomical-Therapeutic-Chemical classification level 3 (ATC3) and preferred name. Summaries will be presented for concomitant therapies taken at baseline and separately those taken after baseline. Separate summaries of use of heart failure-related drugs (e.g. ARNi, beta-blockers, ivabradine, diuretics, ACE-inhibitors, ARBs, MRAs, cardiac glycosides), anticoagulants, acetylsalicylic acid (ASA), or lipid lowering drugs at baseline and newly introduced after baseline will be presented. Use of devices and other non-medication therapy at baseline and newly introduced after baseline will also be summarized. Changes of diuretic therapy over time will be summarized.

Concomitant diseases will be summarised by system organ class and preferred term. Relevant medical history by treatment group will also be presented. Both summaries will be presented using the randomised set.

## **7.3 TREATMENT COMPLIANCE**

Only descriptive statistics are planned for this section of the report. The number and percentage of patients with overall compliance will be reported. Overall compliance will be calculated as a weighted average of reported compliance. The sum of all reported compliance over the planned visits will be divided by the total duration. The treated set of patients will be considered.

## **7.4 PRIMARY ENDPOINT**

The primary estimand of this trial is the hazard ratio of the time to first event of adjudicated HHF or adjudicated CV death between empagliflozin 10 mg and placebo in the population of patients with heart failure with reduced ejection fraction. The primary comparison will be made regardless of changes of treatment (including discontinuation of trial medication) until completion of the planned treatment phase. For clarification, this excludes events and time at risk after the protocol-specified treatment discontinuation for patients that complete the treatment period according to protocol.

### **7.4.1 Primary analysis of the primary endpoint(s)**

As the primary endpoint, time to the first event of adjudicated HHF or adjudicated CV death will be reported in days. The primary analysis will be based on RS, using all data available until completion of the planned treatment phase, including the data after end of treatment for patients not completing the treatment phase as planned.

The primary endpoint will be displayed using cumulative incidence function (CIF) curves and expressed as the hazard ratio with associated two-sided 95% confidence intervals (CIs) and two-sided CIs based available alpha-level for the analysis.

For the interim analysis and final analysis, the following Hwang, Shih and De Cani  $\alpha$ -spending function at information fraction  $t_k$  with parameter  $\gamma = -8$  will be used:

$$\alpha^*(\gamma, t_k) = \min \left\{ \alpha, \quad \alpha \frac{1 - e^{-\gamma t_k}}{1 - e^{-\gamma}} \right\} = \min \left\{ 0.025, \quad 0.025 \frac{1 - e^{8t_k}}{1 - e^8} \right\}$$

The alpha levels are expected to be 0.001 and 0.0248 (one-sided) for the interim and final tests respectively, when the interim analysis occurs at the time of 60% information.

Estimator and corresponding confidence intervals will not be corrected for interim analysis.

The primary endpoint will be analysed using Cox regression, with factors of treatment (empagliflozin, placebo), region (North America, Latin America, Europe, Asia and “other” including India, South Africa and Australia), baseline status of diabetes (diabetes, prediabetes, no diabetes), age (continuous), sex, left ventricular ejection fraction (LVEF) ( $\leq 30\%$ ,  $> 30\%$  to  $\leq 35\%$ ,  $> 35\%$ ) and eGFR (CKD-EPI)cr at baseline (continuous). Since the stratification factors are included in the model as covariates, no stratified Cox regression will be used.

Breslow’s method will be used for dealing with ties.

The individual relevant components of the composite will be summarized descriptively. In this descriptive analysis of the relevant component for the composite, CV death after HHF will not be counted. In all other analyses of CV death alone defined in this document, all CV deaths will be counted, disregarding any earlier events.

A hierarchical testing procedure will be followed for the assessment of the primary and key secondary endpoints. For all endpoints, superiority of empagliflozin vs. placebo will be evaluated using a two-sided test.

The tests will be performed in the following hierarchical order:

1. Time to first event of adjudicated CV death or adjudicated HHF
2. Occurrence of adjudicated HHF (first and recurrent)
3. eGFR (CKD-EPI)cr slope of change from baseline

Starting from step 1, if the null hypothesis of no difference is rejected, and the result is more favourable for empagliflozin, superiority is concluded in the tested endpoint, and the overall type I error is preserved for the test in the next step. If at any step the null hypothesis of no difference is not rejected, subsequent tests are conducted in an exploratory manner.

The overall type I error rate will be preserved at a level of 0.05 (2-sided). The type I error rate used at the final analysis will be influenced by the pre-planned interim analysis.

In the final analysis after the evaluation of recurrent HHF, alpha will be split into 0.001 to be used for the analysis of eGFR slope, and the rest will be transferred to the meta-analyses.

In case the trial is finished early at the time of interim analysis, using  $\alpha_{\text{interim}}$  for the primary and key secondary endpoints in the testing hierarchy according to the  $\alpha$ -spending function above, the following  $\alpha$ -split will be used for the eGFR slope analysis and the meta-analysis:

0.1 \*  $\alpha_{\text{interim}}$  will be used for the eGFR slope analysis and

0.9 \*  $\alpha_{\text{interim}}$  will be transferred to the meta-analyses

In both the interim and final analyses, if the slope analysis is successful, the alpha of this branch will then be transferred to the meta-analyses.

The testing hierarchy is summarized in Figure 7.4.1: 1.

[figure not shown]

Figure 7.4.1: 1 Hierarchical analysis of trial in HFpEF (1245.110) and the parallel trial in HFrEF (1245.121) showing the alpha-spending at the final analysis

#### 7.4.2 Sensitivity analyses, subgroup analysis, exploratory analysis of the primary endpoint(s)

The following sensitivity analyses will be conducted:

- A Cox model including only treatment as covariate, not adjusting for any other variables.
- The same Cox regression as the primary analysis will be performed on the TS, with observation period up to 30 days after treatment discontinuation. Total number of

patients with primary events occurring during the 30 days after treatment discontinuation will also be tabulated.

- For patients who are without primary event and lost to follow up before trial completion, the treatment specific incidence rates for empagliflozin and placebo for retrieved drop-outs will be used to impute the primary events in a multiple imputations framework. The primary model will be applied to the imputed datasets. It is planned to perform 100 imputations. Rubin's rules will be used to summarize the log hazard ratios and the result will be back-transformed to show a hazard ratio with confidence interval.
- The endpoint will be evaluated based on investigator defined events (same model as the primary primary analysis). Investigator defined HHF includes AEs ticked by the investigator as "Hospitalisation due to heart failure". Investigator defined CV death includes AEs ticked by the investigator as "CV death other than CV death attributed to myocardial infarction or stroke", "Undetermined cause of death" as well as HHF, CV hospitalization, MI or stroke if the event was fatal.
- A competing risk model by Fine-Gray will be explored, including the same set of covariates as in the primary analysis, sub-distribution hazard ratios will be provided [\(5\)](#).
- The primary analysis will be repeated to include all events up to individual trial completion including the follow-up period.
- The primary analysis will be repeated to include only confirmed primary events which meet the CDISC guidance criteria for hospitalization for heart failure (i.e., confirmed by adjudication committee, but excluding those missing a physical sign or laboratory test, or both)
- A Cox model including additional prognostic covariates, Log(NTProBNP) and HHF in last 12 months, in addition to the covariates in the primary model.
- A COVID-19 sensitivity analysis will be conducted. The primary analysis will be repeated to include all events up to cutoff dates prior to COVID-19 outbreak – cutoff (censoring) dates are 30Nov2019 for China and 31Dec2019 for all other countries.

A Kaplan-Meier curve of time to censoring for primary endpoint will be presented in order to assess whether there was differential censoring. For this analysis, a primary endpoint event will be counted as censoring and a censoring (including censoring due to the competing event of non-CV death) will be counted as an event.

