7.3.1 Primary endpoint analyses

The primary endpoint will be analysed using a Cox proportional hazards model with age (continuous), gender, treatment, geographical region, baseline status of diabetes (DM, pre-DM, no DM), baseline LVEF ($\leq 30\%$, $>30\%$ to $\leq 35\%$, $> 35\%$) and eGFR (CKD-EPI)_{cr} at baseline (continuous) as covariates.

The time to the event of interest will be calculated by (event date – randomisation date) + 1. All events observed after randomisation until completion of the planned treatment phase will be included in the analysis. Patients who do not have an event during the trial period will be censored at the individual end of the planned treatment phase or the last day that the patient was known to be free of the event, whichever is earlier. Time to censoring will be calculated by (individual end of the planned treatment phase or the last day known to be free of the event – randomisation date) + 1. For patients who have more than one primary endpoint event during the trial, the time to the first occurrence of the primary endpoint event will be considered for the primary analysis. Only the adjudicated and confirmed events are included in the primary analysis.

To detect any heterogeneity in the treatment effect among diabetic patients, pre-diabetic patients and non-diabetic patients, a subgroup analysis will be performed by including diabetic status by treatment interaction term into the Cox model.

Standard subgroup analyses of the primary endpoint include geographical region, sex, BMI, renal function, prognostic factors, age, ethnicity, race and different background therapies etc. More details will be specified in the TSAP.

A sensitivity analysis will be provided based on the treated set but only including any events up to 30 days after treatment discontinuation.

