7.3.2 Secondary endpoint analyses

The key secondary endpoint occurrence of adjudicated HHF (first and recurrent) will be modelled using a joint frailty model together with adjudicated CV death in order to take into account the dependence between the endpoints. The joint frailty model will be adjusted for the same covariates as the primary analysis.

The joint frailty model therefore models the hazards in the following way:

$$r_i(t | \omega_i, Z_i) = \omega_i \exp \{ \beta'_1 Z_i \} r_0(t)$$

$$\lambda_i(t | \omega_i, Z_i) = \omega_i^\alpha \exp \{ \beta'_2 Z_i \} \lambda_0(t)$$

where $r_i(t)$ is the hazard of the recurrent HHF for the i th patient, proportional to the baseline intensity function r_0 . The hazard function of CV death for the i th patient is λ_i proportional to the baseline hazard λ_0 . β_1 and β_2 are vectors of the regression coefficients of the covariate vectors Z_i including treatment, age (continuous), gender, history of DM, geographical region, LVEF (continuous) and eGFR (CKD-EPI)_{cr} at baseline (continuous). Patient specific independent random effects are denoted by ω_i , with α giving the relation between HHF and CV death. Patient specific independent random effects denoted by ω_i and are assumed to follow a gamma distribution with mean 1.

The resulting likelihood function can be solved assuming piecewise constant hazards.

Slope in change from baseline of eGFR (CKD-EPI)_{cr} will be analysed by a random coefficient model allowing for random intercept and random slope per patient. The model will include the factors treatment, gender, geographical region, baseline LVEF, and status of DM as fixed effects and eGFR (CKD-EPI)_{cr} at baseline (continuous), age (continuous), time, interaction of treatment by time, and interaction of eGFR (CKD-EPI)_{cr} at baseline (continuous) by time as linear covariates and allow for randomly varying slope and intercept between patients. The model will include all on-treatment change from baseline data.

Since the slope is run on the change from baseline data, the intercept will model the acute drop, whereas the long-term effect is modelled by the slope.

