5. In all models (e.g., Cox regression, MMRM, et al.) with LVEF included per protocol as a continuous covariate, it has been changed to a categorical variable ( $\leq 30\%$ ,  $>30\%$  to  $\leq 35\%$ ,  $> 35\%$ ). The reason the change was made was because the inclusion criterion has different NTproBNP thresholds depending on presence or absence of atrial fibrillation and LVEF category. This inclusion criterion stipulates that the relationship between LVEF and outcome events is non-monotonic.

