## 7.5 SECONDARY ENDPOINTS

### 7.5.1 Key secondary endpoints

#### 7.5.1.1 Primary analysis of the key secondary endpoints

##### **Occurrence of adjudicated HHF (first and recurrent)**

Hospitalisation for heart failure will be analysed by a joint frailty model (JFM) that accounts for the dependence between recurrent HHF and CV death (7). The primary analysis will be based on all data available until completion of the planned treatment phase, including the data after end of treatment for patients not completing the treatment phase as planned.

Define  $T_{i0} = 0$  and let  $T_{i1}, T_{i2}, \dots, T_{iN_i}$  be the recurrent event times for person  $i$ , where  $N_i$  is the number of recurrent HHF events before  $X_i = \min(C_i, D_i)$ , the minimum of an independent censoring time  $C_i$  and a dependent CV death time  $D_i$ . The JFM is defined through the hazard functions for the recurrent event process and CV death

$$\begin{aligned} r_i(t | \omega_i) &= \omega_i \exp\{\beta_1 z_i\} r_0(t) \\ \lambda_i(t | \omega_i) &= \omega_i^\alpha \exp\{\beta_2 z_i\} \lambda_0(t) \end{aligned}$$

The recurrent heart failure hospitalisations intensity function for the  $i$ -th patient conditional on the patient specific random frailty,  $\omega_i$ , is given by  $r_i$  and is proportional to the baseline intensity function,  $r_0$ . The conditional hazard function for time to CV death for patient  $i$  is given by  $\lambda_i$ , with the baseline hazard given by  $\lambda_0$ , and  $\beta_1, \beta_2$  are  $p \times 1$  vectors of regression coefficients associated with vectors of covariates  $z_i$ . The same covariates as for the analysis of the primary endpoint will be used, e.g.  $\beta_1$ =treatment (empagliflozin, placebo),  $\beta_2$ =region (North America, Latin America, Europe, Asia and “other” including India, South Africa, and Australia),  $\beta_3$ =baseline status of diabetes (diabetes, prediabetes, no diabetes) etc.

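### The primary Cox model could take in log NT-proBNP and recent HHF, already planned as a sensitivity analysis, for a small power gain if no unblinded interim has been run

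*SAP*

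**What the plan says.** Both documents test the primary endpoint with one adjusted Cox model. Protocol 7.3.1 states: "The primary endpoint will be analysed using a Cox proportional hazards model with age (continuous), gender, treatment, geographical region", followed by diabetes status, LVEF in three categories and baseline eGFR. SAP 7.4.1 gives the same set. Neither includes NT-proBNP or a previous hospitalisation for heart failure (HHF).

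SAP 7.4.2 puts these two into a sensitivity analysis: "A Cox model including additional prognostic covariates, Log(NTProBNP) and HHF in last 12 months, in addition to the covariates in the primary model". Both are available at baseline. The Protocol flow chart samples NT-proBNP at Visits 1 and 2, SAP 6.7 takes the last value before first dose, and SAP Table 6.4: 1 lists HHF in the last 12 months as a yes/no variable. SAP 6.6.1 imputes missing covariates, so the richer model loses no patient.

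Other analyses inherit the primary model:
- the interim tests of the primary endpoint and CV death (Protocol 7.4)
- the other Cox endpoints (Protocol 7.3.2 and 7.3.3, SAP 7.5.2)
- the Fine-Gray and subgroup models (SAP 7.4.2 and 7.4.4)
- the joint frailty model for recurrent HHF, where Protocol 7.3.2 says "The joint frailty model will be adjusted for the same covariates as the primary analysis" and SAP 7.5.1.1 says "The same covariates as for the analysis of the primary endpoint will be used"

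SAP 7.4 defines the estimand as follows: "The primary estimand of this trial is the hazard ratio of the time to first event of adjudicated HHF or adjudicated CV death". It does not name the covariates on which that ratio is conditional.

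**The concern.** Baseline variables recognised as prognostic before unblinding usually belong in the model that carries the confirmatory test. Here the SAP calls two variables prognostic, the trial collects both, and the model is already written, but it carries no confirmatory weight.

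The event target stays at 841 whether 2850, about 3600 or 4000 patients are randomised (Protocol 7.7, SAP 9.6). Extra patients bring the events sooner but add none, so the choice of model is one of the few ways left to raise power. The primary test opens the hierarchy: recurrent HHF, the eGFR slope and the alpha passed to the meta-analyses all depend on it.

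**Working it through.** **1. The plan's own figures.** Inputs from Protocol 7.4 and 7.7: HR 0.80, 1:1 allocation, two-sided 0.05 (0.0496 at the final look), 90% power.
- Events (Schoenfeld) = 4(1.960 + 1.282)² / (ln 0.80)² = 845, against 841 stated. The other rows of Table 7.7: 1 give 331, 508, 1592 and 3787, against 330, 508, 1591 and 3786.
- Events from 2850 patients over 18 + 20 months, with placebo hazard −ln(0.85) = 0.1625 per year: 843.
- Power at 841 events and 0.0496: drift d = √(841/4) × |ln HR|. At HR 0.80, d = 14.5 × 0.2231 = 3.236 and Φ(3.236 − 1.963) = 89.8%. At HR 0.75, d = 4.171 and power is 98.6%. SAP 9.6 states 89.98%.

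The current plan is therefore neither mis-sized nor underpowered on its own assumptions.

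**2. Gain from the two covariates.** The documents give no prognostic strengths, so these are assumed. If the richer model multiplies the mean Z by m, the gain is Φ(m·d − 1.963) − Φ(d − 1.963).

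*Simulation A* stops at 841 events, with 2500 runs per case. The SD of the joint log-hazard contribution of the two covariates is 0.20 (weak), 0.51 (moderate) or 0.73 (strong).

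| N | Strength | m | Gain at HR 0.80 | Gain at HR 0.75 |
|---|---|---|---|---|
| 2850 | weak | 1.007 | 0.4 | 0.1 |
| 2850 | moderate | 1.050 | 2.6 | 0.6 |
| 2850 | strong | 1.099 | 4.6 | 0.9 |
| 3600 | weak | 1.005 | 0.3 | 0.1 |
| 3600 | moderate | 1.040 | 2.1 | 0.5 |
| 3600 | strong | 1.082 | 3.9 | 0.8 |

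*Simulation B* applies inclusion criterion 5 to an assumed screened population (median NT-proBNP about 1300 pg/ml, AF 35%, prior HHF 30%), with 3000 runs per case. The hazard ratios per SD of log NT-proBNP / for prior HHF are 1.2/1.2, 1.5/1.3 and 1.9/1.5.
- HR 0.80 in the current model, N = 3600: 90.1% to 90.4%, 89.4% to 91.5%, 89.9% to 94.2% (gains 0.4, 2.1, 4.3). N = 2850: gains 0.6, 2.5, 4.6.
- HR 0.78: gains 0.3, 0.9, 2.8 from about 95%. HR 0.75: gains 0.1, 0.4, 0.9 from about 98.6%.
- A cruder variant without criterion 5, with the lowest 30% of NT-proBNP removed, gave 0.8 (moderate) and 2.8 (strong) at HR 0.80.

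**3. Source of the gain.** In simulation A (strong, N = 2850) the average HR was 0.816 in the current model and 0.799 in the richer one. The ratio of log HRs is 0.2239/0.2035 = 1.10, while the standard errors differ by a factor of 1.001. The richer model estimates a larger conditional effect with essentially the same standard error. If 0.80 is the HR conditional on both covariates, simulation B gives 89.3% to 89.7%, 87.2% to 89.5% and 85.1% to 89.7%, so about 90% is restored and not exceeded.

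**4. Type I error.** Under the null (3000 runs, nominal 4.96% two-sided) both models rejected in 4.9%.

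**5. Interim.** HSD spending with γ = −8 at 60% information is 0.025(1 − e^4.8)/(1 − e^8) = 0.0010, as stated. Stopping also needs CV death to cross. With an assumed 150, 200 or 250 CV deaths and HR 0.80, that criterion alone is met in 4.2%, 6.5% or 9.2% of trials, so no interim benefit is claimed.

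**6. Timing.** On the planning rates the 500th event falls at about month 25 (2850 patients over 18 months), or month 21 to 28 (3600 over 18 to 30 months).

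**The case against.** Several points on the other side stand.

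- **Nothing is broken.** The primary model contains the stratification factors, and models with fewer and with more covariates are already prespecified around it. A reader might infer that the primary analysis is invalid or underpowered. The documents do not support that: its figures reproduce and it holds its error rate.
- **No information is being wasted.** It is tempting to say that adjustment would sharpen the estimate. The standard error barely moves. What changes is the quantity estimated, and the estimand text has to say so.
- **The size is assumed.** In the weak case the gain is about 0.3 to 0.6 points. Protocol 7.7 calls 0.80 conservative, and a stronger true effect shrinks the gain. Covariates stronger than assumed (SD about 0.9) would give 5.4 to 6.5 points at 0.80 and slightly above 1 point at 0.75.
- **The window may be closed.** Amendment 1 (23 Nov 2017) refers to guidance already in the site file, and the latest SAP version is dated 19-JUN-2020, about 31 months later. SAP 9.5 still writes of the interim as future, and no document says it has been run. This makes the proposal conditional but does not defeat it.
- **AF is not in the model.** Eligibility doubles the NT-proBNP thresholds in AF, and the proposal uses one linear log term. With randomised treatment this does not bias the test. It can only limit the gain.
- **Joint frailty convergence.** SAP 7.5.1.1 already provides a fallback for non-convergence, and more covariates could make it likelier. The fix therefore keeps them out of that model.

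A reader might also give weight to Protocol 7.3.2, which ties the joint frailty model to the primary covariates and then lists "gender, history of DM, geographical region, LVEF (continuous) and eGFR". SAP 4 settles this for all models "with LVEF included per protocol as a continuous covariate, it has been changed to a categorical variable". It is leftover text to correct and adds nothing to the case here.

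**Conclusion.** The point holds as a worthwhile improvement to a valid plan. At 841 events the richer model adds about 0.3 to 4.6 points of power at HR 0.80, about 0.3 to 4.3 points at the planned 3600 patients, and under 1 point at HR 0.75. This rests on assumed weak-to-strong prognostic effects and on 0.80 being the HR in the current model. Whether to act depends on one fact that the documents do not give: whether the unblinded interim has been run.

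**What to change.** Confirm the interim status first.

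If no unblinded interim has been run:
- Make the SAP 7.4.2 model (current covariates plus log baseline NT-proBNP and HHF in the last 12 months, yes/no) the primary Cox model for the interim and final tests. Keep the current covariate set as the sensitivity analysis.
- Amend together the Protocol synopsis, 7.3.1 and 7.4, and SAP 4, 7.4, 7.4.1 and 7.4.2. In SAP 7.4, name the covariates on which the estimand's hazard ratio is conditional.
- Let the interim CV-death test and the other Cox endpoints follow the primary model, as the texts already provide.
- In Protocol 7.3.2 and SAP 7.5.1.1, replace the reference to the primary covariates with a named list that keeps the current set with categorical LVEF.
- Check the meta-analysis plans, which are not among these documents, for consistency.

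If the interim has been run, leave the primary model unchanged, so that both looks test with the same model. The leftover continuous LVEF in Protocol 7.3.2 can be corrected either way.

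The cost is a set of linked edits in two documents and a hazard ratio conditional on two more covariates. No new data, visits or events are needed.
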